After enrollment, the research coordinator should complete the demographic information on the Case Report Forms. No fields on the Case Report Forms should be left blank. The research coordinator should also contact and the SLP who will perform the BSE, and the second SLP who will perform the FEES. The research coordinator should arrange a specific time that the BSE and FEES will be performed.

Screening and recruitment techniques:

Every new ICU admission receiving mechanical ventilation will be screened, wherein an established treatment relationship exists. This will include but not be limited to admissions from the ED, wards, and operating room. We will also assess patients transferred from outside hospitals. The enrollment window for these patients will include the time during admission at the outside hospital and during transfer.

The research coordinators or site PI will meet with the new incoming groups of ICU residents as part of their unit orientation. During this time, the residents will be alerted to each of the study inclusion and exclusion criteria. We would also recommend developing printed laminated cards with important study related and contact for the housestaff and other key members of the ICU teams. Each day, the research coordinator will identify each patient who is endotracheally intubated and receiving mechanical ventilation for at least 48 hours. Patients will then be followed until they are extubated.

At the time of extubation, the patient by definition meets inclusion criteria for the study. At this point the patient should be entered into the screening log in one of several ways

1. If they meet a permanent exclusion criteria, they should be entered as be excluded from the study
2. If they meet a potentially transient exclusion (like altered mental status), they should be followed for up to 72 hours after exclusion to determine if the exclusion criteria resolves. If it resolves they should approached for enrollment
3. If the patient meets no exclusion criteria, they should be approached about study participation.
4. If they agree to participate and sign the consent form then they are enrolled into the study.
5. If they decline to participate, then they should be entered as an excluded patient.

Informed consent:

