Next, a SLP will perform a comprehensive BSE on each ARF survivor, and a second blinded SLP will perform the FEES to determine whether aspiration is truly present. The order of the BSE and FEES exams will be randomized. The reason for the random order of the tests is that after several swallows, a patient who has not eaten orally in several days or weeks will start to do better as the system "wakes up". If the BSE always precedes the FEES, it might lead to a false result – it would show more aspiration on the BSE than the FEES. But it won't be because the BSE was showing a false positive; in fact it is just that the patient started to improve by the time he got the second exam.

2. Bedside Evaluation:

The BSE protocol should be performed within 24 hours from the time that the informed consent was signed. The BSE protocol will be performed in the same order and the amount of each bolus delivered in the exact manner for all patients. Unless there are medical restrictions (due to femoral lines, sacral wounds, etc), all BSEs should be performed in a sitting position. The SLP will document the patient position that the BSE was

performed.

Part 1: Initial Assessment: The SLP will review the subject's medical record and become knowledgeable with the patient's medical history. The patient should be seated with the head of the bed as elevated as possible. A physical exam of the aerodigestive system will be performed including respiratory rate; saliva formation; lip seal; tongue movement, strength, and coordination; palate movement, gag reflex; cough reflex; and voice quality/dysphonia. In addition, the SLP will also determine cough strength in L/min using a peak flow meter (HealthScan, Cedar Grove, NJ).

Part 2: Standardized consistency testing: The SLP will then administer five standard consistencies.¹⁰⁶ Some consistencies will be tested twice with different amounts. In general, the bolus should be administered with a medicine cup. A straw should only be used for the 3 ounce water test and the 2 ounce patient controlled trials.

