Part 3: Three Ounce Water Swallow Test (3-WST): During the standardized 3-WST, patients receive three ounces of water and are instructed to drink the entire amount, via cup or straw, completely and without interruption (the cup can be held to the patient's mouth by the SLP).^{74;76;109} The 3-WST will be scored as pass/fail. Criteria for failure of the 3-WST are: the inability to drink the entire amount, coughing or choking up to 1 minute after completion, or the presence of a wet-hoarse vocal quality.

At this point the SLP will document their diet recommendations, and whether further invasive testing (MBSS or FEES) is indicated.

Subsequently, the SLP can perform additional testing including specific maneuvers. The results of these additional tests will be recorded in the CRF. The SLP will then document their diet recommendations that include the knowledge gained from the additional testing. Again the SLP will document whether further invasive testing (MBSS or FEES) is indicated.

Based on these recommendations, the patient will be allowed to advance their diet prior to the performance of the FEES, if indicated.

The coordinator should make sure that the BSE CRF is completely filled out before the SLP who completed the test leaves the ICU.

The BSE form for consistency testing is attached as Appendix.

3. FEES examination: The SLP will review the subject's medical record and become knowledgeable with the patient's medical history. The FEES examination will be performed by a second SLP who is blinded to the results of the BSE. The FEES should be performed within approximately 4 hours of the BSE.

Similar to the BSE, the patient should be seated with the head of the bed as elevated as possible. At the discretion of the SLP/investigator, Afrin and Lidocaine spray can be administered into the nasal passage before the laryngoscope is inserted. The use of these medications will be noted in the case report form.

Part 1: First the SLP will perform and videotape the examination of the upper airway. Velar closure, base of the tongue retraction, laryngeal elevation, right and left vocal cord/arytenoid mobility, right and left pharyngeal wall medialization, epiglottic retroflexion, granuloma formation, and upper airway edema will be assessed.

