Consistent with the above ethical sensibilities regarding the participation of decisionally incapable subjects in research and the previous assessment of risks and benefits in the previous section, the present study presents a balance of risks and potential direct benefits that is *similar* to that available in the clinical setting.

ADDITIONAL SAFEGUARDS FOR VULNERABLE SUBJECTS

The present research will involve subjects who might be vulnerable to coercion or undue influence. As required in 45 CFR 46.111(b), we recommend that additional safeguards be included to protect the rights and welfare of these subjects. Such safeguards might include, but are not limited to: a) assessment of the potential subject's capacity to provide informed consent, b) the availability of the LAR to monitor the subject's subsequent participation and withdrawal from the study; c) augmented consent processes. The specific nature of the additional safeguards will be left to the discretion of the central IRB, in conjunction with the sites.

CONFIDENTIALITY

Federal regulations at 45 CFR 46 111 (a) (7) requires that when appropriate, there are adequate provisions to protect the privacy of subjects and to maintain the confidentiality of data. To maintain confidentiality, all laboratory specimens, evaluation forms, and reports will be identified only by a coded number. The coded number will be generated by a computer, and only the study team will have access to the codes. All records will be kept in a locked, password protected computer. All computer entry and networking programs will be done with coded numbers only. All paper case report forms will be maintained inside a locked office. Study information will not be released without the written permission of the patient, except as necessary for monitoring by the National Heart, Lung, and Blood Institute, and the PETAL Clinical Coordinating Center.

ADVERSE EVENTS

SAFETY MONITORING

Assuring patient safety is an essential component of this protocol. Each participating investigator has primary responsibility for the safety of the individual participants under his or her care. The Investigators will determine daily if any adverse events occur during the period from enrollment through **study day 2** or ICU discharge, whichever occurs first.

The following adverse events will be collected in the adverse event case report forms:

- Serious adverse events

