- Nonserious adverse events that are considered by the investigator to be related to study procedures or of uncertain relationship

A clinical study adverse event is any untoward medical event associated with the study procedure in humans, whether or not it is considered related to a study procedure.

Adverse events related to protocol procedures must be evaluated by the investigator. If the adverse event is judged to be reportable, as outlined above, then the investigator will report to the medical monitor their assessment of the potential relatedness of each adverse event to protocol procedure. Investigators will assess if there is a reasonable possibility that the study procedure caused the event, based on standard criteria. Investigators will also consider if the event is unanticipated or unexplained given the patient's clinical course, previous medical conditions, and concomitant medications.

If a patient's participation in the study is discontinued as a result of an adverse event, study site personnel must report the circumstances and data leading to discontinuation of treatment in the adverse event case report forms.

SERIOUS ADVERSE EVENTS

Serious adverse event collection begins after the patient or surrogate has signed informed consent and has undergone study procedures. If a patient experiences a serious adverse event after consent, but prior to the start of the study, the event will NOT be collected unless the investigator feels the event may have been caused by a protocol procedure.

Study site personnel must alert the medical monitor of any **serious and study procedure related** adverse event within 24 hours of investigator awareness of the event. Alerts issued via telephone are to be immediately followed with official notification on the adverse event case report form.

As per the FDA and NIH definitions, a serious adverse event is any adverse event that results in one of the following outcomes and is not classified as a clinical outcome of acute respiratory failure using the definitions noted above:

- Death
- A life-threatening experience (that is, immediate risk of dying)
- Prolonged inpatient hospitalization or rehospitalization

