As per <http://www.fda.gov/Safety/MedWatch/HowToReport/ucm053087.htm>: Report if admission to the hospital or prolongation of hospitalization was a result of the adverse event. Emergency room visits that do not result in admission to the hospital should be evaluated for one of the other serious outcomes (e.g., life-threatening; required intervention to prevent permanent impairment or damage; other serious medically important event).

- Persistent or significant disability/incapacity

As per <http://www.fda.gov/Safety/MedWatch/HowToReport/ucm053087.htm>: Report if the adverse event resulted in a substantial disruption of a person's ability to conduct normal life functions, i.e., the adverse event resulted in a significant, persistent or permanent change, impairment, damage or disruption in the patient's body function/structure, physical activities and/or quality of life.

Important medical events that may not result in death, be life-threatening, or require hospitalization may be considered serious adverse events when, based upon appropriate medical judgment, they may jeopardize the patient and may require medical or surgical intervention to prevent one of the outcomes listed in this definition.

Serious adverse events will be collected during the first **2 study days** or until ICU discharge, whichever

occurs first, regardless of the investigator's opinion of causation. Thereafter, serious adverse events are not required to be reported unless the investigator feels the events were related to either study drug or a protocol procedure.

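### Adverse-event checks guarantee no observation after the swallow exams, the two safety sections start collection at different points, and the serious-event definition relies on definitions that are absent

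*Combined protocol and SAP*

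**What the plan says.** All references are to the combined protocol and SAP.

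- **General window (Safety Monitoring).** "The Investigators will determine daily if any adverse events occur during the period from enrollment through" study day 2 "or ICU discharge, whichever occurs first". Two kinds of event are collected: serious events, and non-serious events that the investigator thinks related or of uncertain relationship.
- **Enrolment (Screening and recruitment techniques).** "If they agree to participate and sign the consent form then they are enrolled into the study".
- **Exam timing (Study Procedures, items 2 and 3).** "The BSE protocol should be performed within 24 hours from the time that the informed consent was signed", and "The FEES should be performed within approximately 4 hours of the BSE".
- **Serious events, start (Serious Adverse Events).** "Serious adverse event collection begins after the patient or surrogate has signed informed consent and has undergone study procedures". A serious event between consent and the start of the study is collected only if a protocol procedure may have caused it.
- **Serious events, end.** They are collected whatever the cause for two study days or until ICU discharge. "Thereafter, serious adverse events are not required to be reported unless the investigator feels the events were related" to a study drug or a protocol procedure. No end date is set for these.
- **Serious events, definition.** An event counts only if it meets a listed criterion and "is not classified as a clinical outcome of acute respiratory failure using the definitions noted above".
- **Outcome Assessments.** Reintubation with its date, ICU and hospital death, and surgical feeding tube are recorded for every patient. Pneumonia is not listed.

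**The concern.** The study's hazard lies in the exams, yet the general window is counted from consent and can close on ICU discharge. Nothing sets a minimum time under observation after the last test bolus. The protocol lists aspiration among the risks of FEES, and the consequences of an aspirated bolus need not show at the bedside. Pneumonia is the obvious example, and the Significance section itself names it as a consequence of aspiration.

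The exclusion in the serious-event definition adds to this. With no definitions behind it, each investigator decides which events count as outcomes of the underlying illness. Those are the same kinds of event that an aspirated bolus could cause. At stake is whether the safety record can support a statement that the exams were harmless in patients approached within 72 hours of extubation.

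**Working it through.** The plan gives no figure for observation time after the exams, so there is none to reproduce. The check has two parts: a timeline, and a trace of each kind of event through the rules.

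**Timeline.** The latest permitted exam, with the BSE first, is at 24 h (consent to BSE) + about 4 h (BSE to FEES) = about 28 h after consent. Let *h* be the clock time of consent in hours after midnight, and measure from the midnight that starts the consent date. Then time left = window close - (*h* + 28). Because study day is undefined, each reading below is an assumption.

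| Assumed reading | Window closes | Time left | *h* = 0 | 08:00 | 17:00 | 20:00 | just before midnight |
|---|---|---|---|---|---|---|---|
| (a) Day 1 is the date of consent | 48 | 20 - *h* | 20 | 12 | 3 | 0 | about -4 |
| (b) Day 0 is the date of consent | 72 | 44 - *h* | 44 | 36 | 27 | 24 | about 20 |
| (c) 48 elapsed hours from consent | *h* + 48 | 48 - 28 | 20 | 20 | 20 | 20 | 20 |

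Under (a), consent after 20:00 lets the window close before the latest permitted exam. Across (a) to (c) the span is about -4 to 44 h.

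A fourth reading (d) makes day 1 the exam day. If both exams fall on one date and the later is at clock time *e*, the time left is 48 - *e*, which is between 24 and 48 h. If they straddle midnight and day 1 is the date of the first, the later exam is at most about 4 h past midnight. The time left is then at least 24 - 4 = 20 h.

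If FEES comes first, the last exam is the BSE at 24 h, and each figure in (a) to (c) rises by 28 - 24 = 4 h. Reading (a) then runs from 24 down to about 0 h. Under every reading and either order, ICU discharge ends the window early and can leave nothing.

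**Trace through the rules.**

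| Event | Inside the window | After the window |
|---|---|---|
| Non-serious, related or uncertain | Collected | No stated route |
| Serious, judged procedure-related | Collected, with 24-hour alert | Still reportable, no end date |
| Serious, not attributed to a procedure | Collected whatever the cause | Not required |
| Removed by the clinical-outcome exclusion | Not serious; at most a non-serious entry if thought related or uncertain | No stated route |

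The last row follows from where the exclusion sits. It is part of the definition of serious, and both the 24-hour alert and the late-reporting rule apply only to serious events. An excluded event therefore drops out of both.

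No earlier text defines clinical outcomes of acute respiratory failure. The nearest candidate is the Outcome Assessments list, which names fields and defines nothing. If that list were meant, death would be excluded from the serious events although it is the first criterion for one. The same section also refers to a study drug, and this study gives none.

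**The case against.** The strongest reply is that serious harm from the exams is already covered. Serious-event collection starts after study procedures, so it is tied to the exams. A serious event that the investigator links to a procedure stays reportable without limit of time, and the medical monitor must hear within 24 hours of awareness. Reintubation, death and surgical feeding tube are recorded for all patients. An early start at enrolment loses nothing; only the end of the window can. All of this stands, and it narrows the point.

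A reader might infer more than the documents support, in three ways:

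- *That safety collection ignores the exams, so harm from them goes unrecorded.* This is true only of the start of the general window. The serious-event rules and the outcome fields contradict it as a blanket statement.
- *That late related non-serious events are barred.* The text does not exclude them. It gives them no route.
- *That the cited epistaxis rates measure the loss.* 225 x 0.3% to 225 x 0.6% is 0.7 to 1.4, which is the expected total and not the number falling outside the window. Nothing suggests that such bleeding first appears after the window closes.

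It is also fair that the shortest times need late consent, both maximum delays and reading (a). The serious-event text separates consent from the start of the study, which lends some support to reading (d).

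The reply does not close the gap. Late reporting depends on someone noticing and attributing an event after daily checks have stopped. The outcome fields carry no relatedness assessment, and pneumonia has no field. The exclusion can remove an event before either safeguard applies.

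**Conclusion.** The point holds in a limited form. The two safety sections give different start points and must be reconciled. Study day is undefined, and the plan guarantees no observation after the later exam. Counted from consent, the time left after the latest permitted exam is about -4 to 44 h; counted from the exam day it is at least 20 h. ICU discharge can reduce either to zero. These figures take the 24-hour and approximate 4-hour limits at their maximum.

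The exposed events are of three kinds:

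- related non-serious events that appear late;
- serious events that appear late and are not attributed to a procedure, such as pneumonia;
- any event removed by the exclusion that has no definitions behind it.

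The documents give no rate of late harm after the exams, so the number of events lost cannot be stated. The analyses of Aims 1 and 2 are not affected.

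**What to change.** - Use one start point in both safety sections. The first study exam fits the existing serious-event rule and also covers the interval between the two exams.
- Replace study day 2 with the plan's own two days, stated as 48 hours after the later of BSE and FEES, and keep checking after the patient leaves the ICU. Observation after the later exam is then 48 h for every patient who remains in hospital.
- Delete the clinical-outcome exclusion from the serious-event definition. Alternatively, write out the definitions and state that they never apply to an event after an exam that is possibly related to it.

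The cost is protocol wording, a short chart check on the ward, and a few more unrelated events on the forms. Patients are already followed to hospital discharge for outcomes, so no new contact is needed.

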APPENDIX: Case Report Forms

Part 1: BSE Direct Physical Examination

Facial symmetry	Normal	Asymmetric	Not Done	
Lip seal/strength	Complete seal	Reduced Seal/ Weak	Not Done	
Lip movements	Normal	Slow, uncoordinated	Not Done	
Tongue strength/ ROM	Normal/complete	Weak/Reduced	No movement	Not Done
Tongue movements	Normal	Slow, uncoordinated	Not Done	
Dentition	Adequate	Missing teeth	Dentures	Edentulous
Saliva	Normal	Drools at times	Drools constantly	Not Done
Palate/velar elevation	Adequate	Incomplete	Not Done	
Baseline voice	Normal	Aphonic	Hoarse	Wet, gurgly
Baseline Breathing sounds	Normal	Wet	Hoarse/noisy	Stridorous
Respiratory rate (count breaths for 20 seconds and then multiple by 3)	_____ (breaths/min) or Not performed			
Volitional cough	Strong	Weak	Absent	Not done
Volitional cough with peak flow meter	_____ (liters/min) or Not performed			

Part 2: Bolus administration

Study ID:	Date:	Time:
-----------	-------	-------

Note: Determine signs and symptoms of aspiration within 10 seconds after swallowing

Ice Chips (1/2 tsp) Bolus given: YES NO	Signs of Aspiration Can check 1,2, 3, 4, or 5 signs  No aspiration or  Cough/Choking  Throat Clearing  Change in voice  Change in Breath sounds YES NO	Oral Phase Can check 1,2, 3, or 4 signs  Normal or  Prolonged/Slow/Delayed/Cued  Disorganized  Weak (oral residual)  Other impairment Explain: <hr/>	Hyolaryngeal excursion Can check 1, 2, or 3 signs  Normal or  Delayed/Slow  Reduced  Multiple swallows
Ice Chips (full tsp) Bolus given: YES NO	Signs of Aspiration Can check 1,2, 3, 4, or 5 signs  No aspiration or  Cough/Choking  Throat Clearing  Change in voice  Change in Breath sounds YES NO	Oral Phase Can check 1,2, 3, or 4 signs  Normal or  Prolonged/Slow/Delayed/Cued  Disorganized  Weak (oral residual)  Other impairment Explain: <hr/>	
Nectar Thick (5 ml) Bolus given:	Signs of Aspiration Can check 1,2, 3, 4, or 5 signs  No aspiration or	Oral Phase Can check 1,2, 3, or 4 signs  Normal or	

YES NO	 Cough/Choking  Throat Clearing  Change in voice  Change in Breath sounds  Change in Pulse Ox (Greater than 10%)	 Prolonged/Slow/Delayed/Cued  Disorganized  Weak (oral residual)  Other impairment Explain: <hr/>	
Nectar Thick (15 ml)	Signs of Aspiration Can check 1,2, 3, 4, or 5 signs	Oral Phase Can check 1,2, 3, or 4 signs	
Bolus given:	 No aspiration or  Cough/Choking  Throat Clearing  Change in voice  Change in Breath sounds  Change in Pulse Ox (Greater than 10%)	 Normal or  Prolonged/Slow/Delayed/Cued  Disorganized  Weak (oral residual)  Other impairment Explain: <hr/>	
Nectar Thick 2 ounce Patient Controlled With a Straw	Signs of Aspiration Can check 1,2, 3, 4, or 5 signs	Oral Phase Can check 1,2, 3, or 4 signs	
Bolus given:	 No aspiration or  Cough/Choking  Throat Clearing  Change in voice  Change in Breath sounds  Change in Pulse Ox (Greater than 10%)	 Normal or  Prolonged/Slow/Delayed/Cued  Disorganized  Weak (oral residual)  Other impairment Explain: <hr/>	
Puree	Signs of Aspiration Can check 1,2, 3, 4, or 5 signs	Oral Phase Can check 1,2, 3, or 4 signs	Hyolaryngeal excursion Can check 1, 2, or 3 signs

(applesauce) (5 ml)	 No aspiration	 Normal	 Normal
	or  Cough/Choking  Throat Clearing  Change in voice  Change in Breath sounds  Change in Pulse Ox (Greater than 10%)	 Prolonged/Slow/Delayed/Cued  Disorganized  Weak (oral residual)  Other impairment	 Delayed/Slow  Reduced  Multiple swallows
Stethoscope used for auscultation		Explain: _____	
	YES NO		
Puree (applesauce) (15 ml)	Signs of Aspiration Can check 1,2, 3, 4, or 5 signs  No aspiration or  Cough/Choking  Throat Clearing  Change in voice  Change in Breath sounds  Change in Pulse Ox (Greater than 10%)	Oral Phase Can check 1,2, 3, or 4 signs  Normal or  Prolonged/Slow/Delayed/Cued  Disorganized  Weak (oral residual)  Other impairment	
	YES NO	Explain: _____	
Thin Liquid (water) (5 ml) or a tsp	Signs of Aspiration Can check 1,2, 3, 4, or 5 signs  No aspiration or  Cough/Choking  Throat Clearing  Change in voice  Change in Breath sounds  Change in Pulse Ox (Greater than 10%)	Oral Phase Can check 1,2, 3, or 4 signs  Normal or  Prolonged/Slow/Delayed/Cued  Disorganized  Weak (oral residual)  Other impairment	
	YES NO	Explain: _____	
Stethoscope used for auscultation			
	YES NO		

	(Greater than 10%)		
Thin Liquid (water) (15 ml)	
Signs of Aspiration Can check 1,2, 3, 4, or 5 signs
 
 No aspiration or  Cough/Choking  Throat Clearing  Change in voice  Change in Breath sounds  Change in Pulse Ox (Greater than 10%)
	
Oral Phase Can check 1,2, 3, or 4 signs
 
 Normal or  Prolonged/Slow/Delayed/Cued  Disorganized  Weak (oral residual)  Other impairment
	
Bolus given: YES NO		Explain: _____	
Stethoscope used for auscultation			
Thin Liquid (Water)	
Signs of Aspiration Can check 1,2, 3, 4, or 5 signs
 
 No aspiration or  Cough/Choking  Throat Clearing  Change in voice  Change in Breath sounds  Change in Pulse Ox (Greater than 10%)
	
Oral Phase Can check 1,2, 3, or 4 signs
 
 Normal or  Prolonged/Slow/Delayed/Cued  Disorganized  Weak (oral residual)  Other impairment
	
2 Oz Patient controlled With a straw		Explain: _____	
Bolus Given: YES NO			
Stethoscope used for auscultation			
Solid (1/4 graham cracker)	
Signs of Aspiration Can check 1,2, 3, 4, or 5 signs
 
 No aspiration or  Cough/Choking  Throat Clearing  Change in voice
	
Oral Phase Can check 1,2, 3, or 4 signs
 
 Normal or  Prolonged/Slow/Delayed/Cued  Disorganized  Weak (oral residual)
	
Bolus given: YES NO			
Stethoscope used			

for auscultation YES NO	 Change in Breath sounds	 Other impairment	Explain: _____
	 Change in Pulse Ox (Greater than 10%)		

Part 3. 3 oz Water Swallow Test (Yale Protocol)

Patient is given a cup with 3 oz water. He is asked to drink the entire amount, slowly and steadily, *but without stopping*. (use your judgment). He can drink from the cup with a straw and the SLP can hold the cup or straw

Was the 3 oz water test performed? YES NO

If yes complete the following table.

Patient stopped 1+ times?	Patient failed to drink the entire amount?	Cough/Choking?	Change in Voice??	Change in Breath Sounds?	No signs of aspiration
 Yes  No					

RESULTS of 3 oz water test? PASS FAIL

Pass= drinks the entire amount without stopping (use your judgment), and without coughing, choking during or immediately after completion.

Fail = does not finish the total amount, stops 1+ times (for more than a few seconds), or has overt signs of aspiration immediately after swallowing

SUMMARY OF CLINICAL EXAM

Results:

Dysphagia detected? Yes/no (oral or pharyngeal)

Aspiration detected? Yes/no

Diet texture recommendations (circle one)

Solids: regular (NDD3) mechanical (NDD2) puree (NDD1) npo

Liquids thin nectar honey npo

Part 4: Scoring Sheet for the FEES Testing

R 21 FEES Evaluation Form		
Study ID:	Date:	Time:

MAKE SURE THE ENTIRE EXAMINATION IS VIDEOTAPED

Afrin spray used: **YES** **NO**

Topical lidocaine used: **YES** **NO**

Velar Closure (hiss like a snake)	 Complete  Incomplete  N/A
Base of Tongue Retraction (Paul is tall)	 Present  Absent  N/A
Right Vocal Cord/Arytenoid Mobility	 None  Mild  Moderate  Severe  N/A
Left Vocal Cord/Arytenoid Mobility	 None  Mild  Moderate  Severe  N/A
Glottic Closure (breath hold, cough, phonation)	 Complete  Incomplete  N/A
Laryngeal Elevation/ Arytenoid lift (glide with an “eee”)	 Present  Absent  N/A
Right Pharyngeal Wall Medialization	 Complete  Reduced  Absent  N/A
Left Pharyngeal Wall Medialization	 Complete  Reduced  Absent  N/A
Epiglottic Retroflexion (during swallow)	 Complete  Reduced  Inconsistent  Absent  N/A
Granuloma Formation	 None  Mild  Moderate  Severe  N/A
Upper Airway Edema	 None  Mild  Moderate  Severe  N/A

Right Laryngeal Sensation touch on the aryepiglottic fold, if no sensation then repeat x1;	None	Mild	Moderate	Severe	N/A
Left Laryngeal Sensation touch on the aryepiglottic fold, if no sensation then repeat x1;	None	Mild	Moderate	Severe	N/A

Ice Chips (1/2 tsp)	PAS score <hr/>	Swallowing Onset Time <hr/>	Incomplete bolus clearance							
			Yes No							
Bolus given: YES NO	Not Determined	Not Done	Not Determined							
	If penetration (2-5): 
 
Before Swallow	During Swallow	
 
After Swallow		
 
 If aspiration (6-8): 
 
Before Swallow	During Swallow	
 
After Swallow		
 
	Before Swallow	During Swallow	After Swallow		Before Swallow	During Swallow	After Swallow		
Before Swallow	During Swallow									
After Swallow										
Before Swallow	During Swallow									
After Swallow										
Ice Chips (full tsp)	PAS score <hr/>	Swallowing Onset Time <hr/>	Incomplete bolus clearance							
			Yes No							
Bolus given: YES NO	Not Determined	Not Done	Not Done							
	If penetration (2-5): 
 
Before Swallow	During Swallow	
 
After Swallow		
 
 If aspiration (6-8): 
 
Before Swallow	During Swallow	
 
After Swallow		
 
	Before Swallow	During Swallow	After Swallow		Before Swallow	During Swallow	After Swallow		
Before Swallow	During Swallow									
After Swallow										
Before Swallow	During Swallow									
After Swallow										
Nectar Thick (5 ml) or 1 tsp	PAS score <hr/>	Swallowing Onset Time <hr/>	Incomplete bolus clearance							
			Yes No							
Bolus given: YES NO	Not Determined	Not Done	Not Done							
	If penetration (2-5): 
 
Before	During	
 
	Before	During		Residue location: Circular all that apply					
Before	During									

	
 
Swallow	Swallow	
 
After Swallow	
 
If aspiration (6-8)	
 
 Before Swallow	During Swallow	
 
After Swallow	
 
	Swallow	Swallow	After Swallow		If aspiration (6-8)		Before Swallow	During Swallow	After Swallow			
 
BOT	valleculae	Lateral channels	
 
piriforms	Laryngeal vestibule		
 
	BOT	valleculae	Lateral channels	piriforms	Laryngeal vestibule	
Swallow	Swallow																		
After Swallow																			
If aspiration (6-8)																			
Before Swallow	During Swallow																		
After Swallow																			
BOT	valleculae	Lateral channels																	
piriforms	Laryngeal vestibule																		
			Response to residue:																
			
 
Spontaneous clearing	None	
 
	Spontaneous clearing	None														
Spontaneous clearing	None																		
Nectar Thick (15 ml)	PAS score <hr/>	Swallowing Onset Time <hr/>	Incomplete bolus clearance																
Bolus given:	Not Determined	Not Done	Yes No																
YES NO	If penetration (2-5):		Not Done																
	
 
Before Swallow	During Swallow	
 
After Swallow	
 
	Before Swallow	During Swallow	After Swallow			Residue location: Circular all that apply												
Before Swallow	During Swallow																		
After Swallow																			
	
 
Before Swallow	During Swallow	
 
After Swallow	
 
	Before Swallow	During Swallow	After Swallow			
 
BOT	valleculae	Lateral channels	
 
piriforms	Laryngeal vestibule		
 
	BOT	valleculae	Lateral channels	piriforms	Laryngeal vestibule							
Before Swallow	During Swallow																		
After Swallow																			
BOT	valleculae	Lateral channels																	
piriforms	Laryngeal vestibule																		
			Response to residue:																
			
 
Spontaneous clearing	None	
 
	Spontaneous clearing	None														
Spontaneous clearing	None																		
Nectar Thick 2 ounce Patient Controlled With a Straw	PAS score <hr/>	Swallowing Onset Time <hr/>	Incomplete bolus clearance																
Bolus given:	Not Determined	Not Done	Yes No																
YES NO	If penetration (2-5):		Not Done																
	
 
Before Swallow	During Swallow	
 
After Swallow	
 
	Before Swallow	During Swallow	After Swallow			Residue location: Circular all that apply												
Before Swallow	During Swallow																		
After Swallow																			
	
 
Before Swallow	During Swallow	
 
After Swallow	
 
	Before Swallow	During Swallow	After Swallow			
 
BOT	valleculae	Lateral channels	
 
piriforms	Laryngeal vestibule		
 
	BOT	valleculae	Lateral channels	piriforms	Laryngeal vestibule							
Before Swallow	During Swallow																		
After Swallow																			
BOT	valleculae	Lateral channels																	
piriforms	Laryngeal vestibule																		
			Response to residue:																
			
 
Spontaneous clearing	None	
 
	Spontaneous clearing	None														
Spontaneous clearing	None																		

Puree (applesauce) (5 ml) Bolus given: YES NO	PAS score <hr/>	Swallowing Onset Time <hr/> Not Done	Incomplete bolus clearance 
 
 Yes	No	
 
	Yes	No												
Yes	No																
Not Determined If penetration (2-5): 
 
 Before Swallow	During Swallow	
 
 After Swallow	
 
 If aspiration (6-8) 
 
 Before Swallow	During Swallow	
 
 After Swallow	
 
	Before Swallow	During Swallow	After Swallow		Before Swallow	During Swallow	After Swallow		Not Done Residue location: Circular all that apply 
 
 BOT	valleculae	Lateral channels	
 
 piriforms	Laryngeal vestibule		
 
 Response to residue: 
 
 Spontaneous clearing	None	
 
	BOT	valleculae	Lateral channels	piriforms	Laryngeal vestibule		Spontaneous clearing	None
Before Swallow	During Swallow																
After Swallow																	
Before Swallow	During Swallow																
After Swallow																	
BOT	valleculae	Lateral channels															
piriforms	Laryngeal vestibule																
Spontaneous clearing	None																
Puree (applesauce) (10 ml) Bolus given: YES NO	PAS score <hr/>	Swallowing Onset Time <hr/> Not Done	Incomplete bolus clearance 
 
 Yes	No	
 
	Yes	No												
Yes	No																
Not Determined If penetration (2-5): 
 
 Before Swallow	During Swallow	
 
 After Swallow	
 
 If aspiration (6-8) 
 
 Before Swallow	During Swallow	
 
 After Swallow	
 
	Before Swallow	During Swallow	After Swallow		Before Swallow	During Swallow	After Swallow		Not Done Residue location: Circular all that apply 
 
 BOT	valleculae	Lateral channels	
 
 piriforms	Laryngeal vestibule		
 
 Response to residue: 
 
 Spontaneous clearing	None	
 
	BOT	valleculae	Lateral channels	piriforms	Laryngeal vestibule		Spontaneous clearing	None
Before Swallow	During Swallow																
After Swallow																	
Before Swallow	During Swallow																
After Swallow																	
BOT	valleculae	Lateral channels															
piriforms	Laryngeal vestibule																
Spontaneous clearing	None																
Thin Liquid (Water) (5 ml) Bolus given: YES NO	PAS score <hr/>	Swallowing Onset Time <hr/> Not Done	Incomplete bolus clearance 
 
 Yes	No	
 
	Yes	No												
Yes	No																
Not Determined If penetration (2-5): 
 
 Before Swallow	During Swallow	
 
 After Swallow	
 
	Before Swallow	During Swallow	After Swallow		Not Done Residue location: Circular all that apply 
 
 BOT	valleculae	Lateral channels	
 
	BOT	valleculae	Lateral channels									
Before Swallow	During Swallow																
After Swallow																	
BOT	valleculae	Lateral channels															

	If aspiration (6-8) 

Before Swallow	During Swallow	

After Swallow	

	Before Swallow	During Swallow	After Swallow			

piriforms	Laryngeal vestibule	

	

	piriforms	Laryngeal vestibule										
Before Swallow	During Swallow																		
After Swallow																			
piriforms	Laryngeal vestibule																		
			Response to residue: 

Spontaneous clearing	None	

	Spontaneous clearing	None														
Spontaneous clearing	None																		
Thin Liquid (Water) (15 ml)	PAS score _____	Swallowing Onset Time _____	Incomplete bolus clearance 

Yes	No	

	Yes	No														
Yes	No																		
Bolus given: YES NO	Not Determined If penetration (2-5): 

Before Swallow	During Swallow	

After Swallow	

 If aspiration (6-8) 

Before Swallow	During Swallow	

After Swallow	

	Before Swallow	During Swallow	After Swallow		Before Swallow	During Swallow	After Swallow		Not Done	Not Done Residue location: Circular all that apply 

BOT	valleculae	Lateral channels	

piriforms	Laryngeal vestibule		

 Response to residue: 

Spontaneous clearing	None	

	BOT	valleculae	Lateral channels	piriforms	Laryngeal vestibule		Spontaneous clearing	None
Before Swallow	During Swallow																		
